9.3.2. Unsolicited Adverse Events

The proportion of subjects reporting at least one unsolicited adverse event will be summarized by MedDRA system organ class and preferred term for each vaccination and over all vaccinations. Denominators for percentages are the number of subjects who received the vaccination being summarized.

Adverse events by subject will be presented in Listing 10.

The following summaries for unsolicited adverse events will be presented by MedDRA system organ class, preferred term, vaccination and treatment group:

- Summary of adverse events occurring in 5% of subjects (Table 26);
- Subject incidence and total frequency of adverse events over time with 95% CI (Day 1-8, Day 9-29 (pre-vaccination), Day 29 (post-vaccination)-36, Day 37-57, Day 180-187, Day 188-208, Day 209-360, and anytime post-any dose) (Table 39 and Table 40);
- Summary of severity and relationship to study product (Table 41);
- Subject incidence and total frequency of related adverse events over time (Day 1-8, Day 9-29(pre-vaccination), Day 29 (post-vaccination)-36, Day 37-57, Day 180-187, Day 188-208, Day 209-360, and anytime post-any dose) (Table 42 and Table 43);
- Subject listing of non-serious adverse events of moderate or greater severity (Table 45);

- Bar chart of the frequency of serious and non-serious related adverse events by severity and MedDRA system organ class (Figure 19);
- Bar chart of the incidence of serious and non-serious related adverse events by maximum severity and MedDRA system organ class (Figure 20);

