Subjects will be observed for 30 minutes after vaccination. The occurrence of solicited injection site and systemic reactogenicity events will be measured from the time of study vaccination through Day 8 after each vaccination. These will be ascertained through use of an electronic Memory (e-Memory) aid, a telephone call on Day 4 after each dose of vaccine, a Day 8 clinic visit, and potentially at the Day 15 clinic visit after each dose of vaccine. Unsolicited AEs will be collected from vaccination through D29 after each vaccination. SAEs will be collected from the time of the first study vaccination through the last study visit (Day 360).

The study includes multiple phlebotomy time points for immunogenicity and blood collection for future use at Visit 1 and Days 8, 15, and 29 after each vaccination. The durability of the immune response and future use collection will be assessed at 5 months after the first boost (Day 180) and at 6 months after the second boost (Day 360).

Note: The study day and the day after boost vaccination may not always align due to the study windows (See Appendix A) for the appropriate windows of time for each study visit.

Schematic of Study Design: See Figure 1.

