3.3 Study Endpoints or Outcome Measures

3.3.1 Primary

- Determine the number of solicited local and systemic reactogenicity events from the time of study vaccination through D8 after each study vaccination.
- Determine the number of vaccine-related unsolicited adverse events (AE) from the time of each study vaccination through D29 after each study vaccination.
- Determine the number of clinical safety laboratory AEs at Day 8 after each study vaccination.
- Determine the number of vaccine-related serious adverse event (SAE) from the time of first study vaccination through 6 months after the last dose of vaccine.
- Determine the number of subjects showing ≥4 fold rise in serum HEV IgG concentration by ELISA from the baseline at Days 8, 15, 29, 36, 43, 57, 180, 187, 194, 208, and 360.

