5.2 Requirements Prior to Administration of the Second and Third Vaccinations

The following assessments should be performed prior to the administration of the second and third vaccinations to determine if the subject remains eligible:

Subjects will not receive the subsequent vaccine doses (first or second boost) if any of the prespecified individual halting criteria are met (see below and Section 8.6.2).

- For a woman of childbearing potential, an acceptable form of birth control must be verified. A urine pregnancy test must be performed and the subject must not be pregnant before administering the vaccine.
- Subjects who do not meet inclusion criteria 2 4 and 7 11, and exclusion criteria 7 21 will not be given the second or third vaccination.
- Subjects who have a fever (defined as an oral temperature ≥38.0°C) or a moderate or severe acute illness at the time of or in the three days prior to boost vaccination administration may have the boost vaccination deferred until they recover as long as this remains within the study window (see Section 6.3).
- Subjects who do not receive the second dose of vaccine for any reason will not receive the third dose of vaccine.

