5.3.2 Subject Replacement

Subjects who withdraw, or are withdrawn or terminated from this trial, or are lost to follow-up after signing the informed consent form (ICF), randomization and receipt of study vaccine will not be replaced. However, if a subject withdraws after signing the ICF, but before randomization and/or receipt of study vaccine, they may be replaced.

DMID/NIAID/NIH

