6.3.1.10 Visit 11, Day 180 +/- 14 Days from Prime Vaccination; Clinic Visit

Prior to Vaccination

- Review medical history for any interval changes
- Review concomitant medications
- Obtain vital signs (HR, BP, and oral temperature)
- Subjects who have a diastolic blood pressure value >90 mmHg or a systolic blood pressure value >140 mmHg prior to the prime vaccination can receive the vaccination if the elevated blood pressure is considered to be not clinically significant and the subject had acceptable blood pressure at screening.
- Perform symptom-directed PE (if needed).
- Perform urine pregnancy test for women of childbearing potential within 24 hours prior to immunization. Test result must be known and negative prior to vaccination.
- Review of birth control history with female subjects.

DMID/NIAID/NIH

- Counsel subjects to use adequate birth control methods to avoid pregnancy.
- Obtain blood for safety laboratories (Section 2.3.1).
- Obtain serum for immunogenicity assays.
- Collect PBMCs and plasma for future assays
- Review inclusion and exclusion criteria to ensure the subject remains eligible for boost vaccination
- Study vaccine will be prepared on-site by an unblinded site research pharmacist (see Section 4.3).
- Pre-administration reactogenicity assessments will be performed prior to vaccination to establish baseline. A subject with mild pre-administration reactogenicity which is transient, resolving, or clinically insignificant may receive vaccination at the investigator's discretion.

Vaccination

- The unblinded study vaccine administrator will vaccinate the subject according to vaccination assignment in the subject's preferred arm.
- Following receipt of study product, subjects may have the injection site covered with an adhesive bandage (e.g. BAND-AID®) as needed.

Following Vaccination

- Observe subjects for a minimum of 30 minutes following immunization.

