8.2 Specification of Safety Parameters

Safety will be assessed by the frequency and severity of:

- 1. Serious adverse events (see Section 8.1.4) occurring from the time of the first study vaccination through the last study visit (Day 360).
- 2. Solicited Adverse Events (see Section 8.1.2) reactogenicity events occurring on the day of each study vaccination through Day 8 after each study vaccination:

DMID/NIAID/NIH

a) Injection site reactions including pruritus (itching), ecchymosis (bruising), erythema (redness), induration (hardness)/swelling, pain, and tenderness.

b) Systemic reactions including fever, feverishness (chills/shivering/sweating), fatigue (tiredness), malaise (general unwell feeling), myalgia (body aches/muscular pain exclusive of the injection site), arthralgia (joint pain exclusive of the injection site), headache, nausea, and vomiting.

- 3. Clinical safety laboratory AEs (see **Appendix B**) at Day 8 after each study vaccination. Parameters to be evaluated include WBC, ANC, AEC, Hgb, PLT, Cr, and ALT (Section 2.3.1).
- 4. Unsolicited Adverse Events (see Section 8.1.3) non-serious adverse events occurring from the time of the first study vaccination until Day 57 then from Day 180 through Day 208. Unsolicited AEs will be collected at all visits from the time of the first study vaccination until D57, then from Day 180 through 208. Any safety-related changes that occur post-vaccination during these timeframes and that represent an increase in grade must be recorded on the eCRF. Thereafter, recording will be limited to SAEs.

All Grade 1, 2, and 3 changes except for Grade 1 and 2 solicited adverse events must be assessed for relatedness to the study vaccination. The assessment of causality must be determined by a study clinician licensed to make medical diagnoses and listed on the FDA Form 1572 as the site principal investigator or sub-investigator.

8.3 **Reporting Procedures**

Solicited injection site and systemic reactogenicity events will be documented and reported from the time of each study vaccination through D8 after each study vaccination.

Unsolicited non-serious AEs will be documented and reported at all visits from signing of the ICF onwards until D57, then from Day 180 through Day 208.

SAEs will be collected from the time of the first study vaccination through the last study visit (Day 360).

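### The by-dose unsolicited-AE tables use fixed study days with no stated day convention, note a Safety Population N against the SAP's per-dose denominator, and omit a promised any-time column

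*SAP*

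**What the plan says.** **Dose-anchored text.** Protocol 3.3.1 counts vaccine-related unsolicited AEs "from the time of each study vaccination through D29 after each study vaccination", and SAP 3.2.1 repeats this. Protocol 3.1 agrees: "Unsolicited AEs will be collected from vaccination through D29 after each vaccination". It also warns: "The study day and the day after boost vaccination may not always align due to the study windows". Protocol 6.3.1.10 gives the dose-3 window as "Visit 11, Day 180 +/- 14 Days from Prime Vaccination; Clinic Visit", that is Day 166 to Day 194.

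**Fixed-day text.** The interval list in SAP 9.3.2 ends "Day 180-187, Day 188-208, Day 209-360, and anytime post-any dose) (Table 39 and Table 40", and the same intervals are given for related events in Tables 42 and 43. The shells place them under Post Dose 1, 2 and 3 headings. Footnotes a and b split Day 29 at receipt of dose 2; nothing similar covers Day 180. Protocol 8.2, 8.3 and 8.4, Appendix A note m and SAP 4.5.1 also state collection in fixed days: to Day 57, then Day 180 to Day 208. Protocol 8.2 adds: "Thereafter, recording will be limited to SAEs".

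**Denominator.** SAP 9.3.2 divides by the subjects who received the vaccination being summarised. The notes to Tables 39 and 42 (and so 40 and 43, which copy their format) define N as the Safety Population. So does the note to Table 27 for solicited events. The notes to Tables 28-36 and 38 are dose-specific.

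**Any-time column.** SAP 9.3.2 promises one in Tables 39, 40, 42 and 43. The Table 39 shell has it. The Table 42 shell, which Table 43 copies, stops at Day 209-360.

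**The concern.** The first primary objective is safety after each dose, and Tables 42 and 43 are the only tabulated summaries of related unsolicited AEs by dose. Two programmers working from this text could fill them differently, because one set of passages counts from the dose and another counts in fixed days. The single windowing rule, in SAP 4.5, concerns assessment values at visits and does not settle AE onset.

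The denominator matters because dose-3 recipients can be fewer than the Safety Population. Protocol 5.2 states: "Subjects who do not receive the second dose of vaccine for any reason will not receive the third dose of vaccine". Under protocol 5.3.2, subjects who leave after "randomization and receipt of study vaccine will not be replaced". A Safety Population N would then make dose-2 and dose-3 percentages, and the zero-event upper limits, too low.

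Without an any-time column, a related SAE with onset between Day 57 and Day 180 has no place in Tables 42 or 43.

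**Working it through.** **Inputs.** Dose-3 window Day 166-194 (protocol 6.3.1.10); dose-2 window Day 29 +/- 2 (protocol 6.3.1.4); endpoint window Days 1-29 after each dose (protocol 3.3.1); intervals from SAP 9.3.2; arms of 20 and 5 (protocol 10.2).

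**Step 1: reproduce the interval edges.** For a dose on study day T, post-dose day k is study day T + k - 1. With T = 180, k = 8 gives 187 and k = 29 gives 208. These match the Visit 13 and Visit 15 labels in the protocol, so the intervals are exact when dose 3 falls on Day 180.

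**Step 2: move dose 3, reading the intervals as calendar days.** Days 1-8 belong in 180-187 and Days 9-29 in 188-208. With dose 3 on Day 180 + d, |d| days fall outside 180-208 and min(|d|, 8) fall in the wrong one of the two intervals. Correct days = 29 - |d| - min(|d|, 8).

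| Dose 3 on Day | Correct | Wrong interval within 180-208 | Outside 180-208 |
|---|---|---|---|
| 180 | 29 | 0 | 0 |
| 179 or 181 | 27 | 1 | 1 |
| 173 or 187 | 15 | 7 | 7 |
| 166 or 194 | 7 | 8 | 14 |

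- Dose on Day 194: Days 16-29 after the dose are study Days 209-222 and fall in 209-360. The 194 - 180 = 14 pre-dose days 180-193 sit under Post Dose 3.
- Dose on Day 166: the first 14 days (study Days 166-179) fall in no by-dose column.
- Dose 2 on Day 27 or 31: 25 of 29 days are correct.

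**Step 3: nominal reading.** If Day 180 means the actual day of dose 3, all 29 days are correct for every allowed dose day.

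These are counts of days, not events. The documents give no distribution of actual dose days.

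**Step 4: denominator.** With no events, the Clopper-Pearson 95% upper limit is 1 - 0.025^(1/n).

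- Vaccine arm: n = 20 gives 16.8%, n = 18 gives 18.5%, n = 16 gives 20.6%.
- Placebo arm: n = 5 gives 52.2%, n = 4 gives 60.2%.
- One subject with an event: 1/20 = 5.0% (95% CI 0.1-24.9); 1/18 = 5.6% (0.1-27.3). Under the whole-number rule in SAP 13 these print as 5% and 6%.

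The reduced recipient counts are assumptions: 18 of 20 with a range of 16 to 20, and 4 of 5 for placebo. Tables 27, 39 and 40 carry confidence intervals; Tables 42 and 43 carry percentages only.

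**The case against.** The strongest reply is that the intended reading is clear. Days 36, 57, 187 and 208 are the protocol's own labels for Days 8 and 29 after each boost. Appendix A maps Day 180 to Day 1 from the third vaccine, the columns are headed by dose, and Day 29 is split at receipt of dose 2. Putting pre-dose days under Post Dose 3 would contradict the heading. This largely stands: nominal days are the better reading. A reader might infer that the tables will misclassify events, but the documents do not show that. What remains is that no sentence states the convention for AEs, and five passages put collection itself in fixed days, so the calendar reading is not contrived.

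On the denominator, SAP 6.1 has tables annotated with the relevant population size, and each Table 39 column has its own N. The note could therefore name the population and leave the divisor to SAP 9.3.2. That is possible, but the note defines N without limiting it to dose recipients, as the notes to Tables 28-36 do. It would also be too strong to say that Table 27 breaks a rule: SAP 9.3 allows either the Safety Population or recipients of a given dose, as appropriate. Table 27 is out of line with its neighbours, nothing more.

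On the missing column, a reader might infer that information is lost. It is not. Event counts add across intervals, with Table 44 supplying SAEs between Day 57 and Day 180, and Table 41 gives related subjects per preferred term.

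**Conclusion.** The point holds as a gap in specification confined to the by-dose displays. Three things need repair: an unstated day convention beside conflicting fixed-day collection wording, table notes that disagree with the SAP's per-dose denominator, and one promised column missing from two shells.

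On the nominal reading the first has no effect; on the calendar reading it leaves 7 to 27 of 29 days correctly placed at the three offsets tabulated. The denominator has no effect if everyone receives every dose, and about 1.7 percentage points on the zero-event upper limit (18.5 - 16.8) if 18 of 20 vaccinees receive dose 3.

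The primary safety results as a whole are not at risk. Tables 25, 41, 44 and 45, Figures 19-20 and Listing 10 do not depend on the day intervals. It is still worth fixing before programming, because following the fixed-day text or the notes literally would misplace or drop endpoint days after dose 3, or understate per-dose rates.

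**What to change.** 1. In SAP 9.3.2 and Tables 39, 40, 42 and 43, define intervals by days since the subject's actual most recent dose: D1-8 and D9-29 after each dose, then D30 onward after dose 3. Extend the second dose-1 interval to receipt of dose 2 when that falls after D29. With dose 2 on Day 31, Day 30 and the pre-dose part of Day 31 would otherwise have no column. Events after dose 2 count under dose 2.
2. Send SAEs between D29 after dose 2 and dose 3 to a stated column or to the any-time column.
3. Set N in each by-dose column of Tables 27, 39, 40, 42 and 43 to Safety Population subjects who received that dose. Keep the full Safety Population N for the any-time column.
4. Reconcile the Table 28 note with SAP 9.3.1, which uses subjects with non-missing data for the event.
5. Add the any-time column to Tables 42 and 43.
6. Reword Table 39 footnote c, which speaks of all AEs through Day 360, to say that only SAEs are recorded after Day 29 post dose 3.
7. Reconcile the fixed-day collection wording (protocol 8.2, 8.3, 8.4, Appendix A note m, SAP 4.5.1) with protocol 3.1 and the endpoint window.

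The cost is SAP wording, labels and notes, one column in two shells, and a protocol clarification. Post-dose visits are already timed from the dose and Listing 10 already holds dose number and days post dose, so no new visits or data are needed.

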9.4. Deaths, Serious Adverse Events and other Significant Adverse Events

The following listings will be presented including Subject ID, Adverse Event Description, Last Dose Received/Days Post Dose, Reason Reported as an SAE, Relationship to Treatment, Alternate Etiology if not Related, Outcome, and Duration of Event (days):

• Deaths and Serious Adverse Events (Table 44);

9.5. Pregnancies

For any subjects in the Safety population who become pregnant during the study, every attempt will be made to follow these subjects to completion of pregnancy to document the outcome, including information regarding any complications with pregnancy and/or delivery. A table summarizing the total pregnancies, number of live births, and number of spontaneous abortions, elective abortions or still births by treatment will be presented. In addition, a listing of pregnancies and outcomes will be presented (Listing 16, Listing 17, Listing 18, Listing 19, and Listing 20).

9.6. Clinical Laboratory Evaluations

Clinical safety laboratory parameters will be collected at Baseline (screening visit) and Study Days 8, 36, 180, and 187. If indicated by symptoms they may also be evaluated at Study Day 15, 43, 194 or at Early Termination/Unscheduled visits.

Chemistry parameters to be evaluated include creatinine and alanine aminotransferase (ALT). Hematology parameters to be evaluated include white blood cell count (WBC), absolute neutrophil count (ANC), the absolute eosinophil count (AEC), hemoglobin, and platelets. Grading scales for safety laboratory parameters are presented in Table 6.

The distribution of laboratory results by severity, time point, and treatment group will be presented in Table 48, Table 49, Table 50, Table 51, Table 52, and Table 53 for chemistry and beginning at Table 56 and concluding at Table 67 for hematology. Descriptive statistics including mean, standard deviation, median, minimum and maximum values by time point, for each laboratory parameter, will be summarized in Table 54, Table 55, Table 68, Table 69, Table 70, Table 71, and Table 72. Changes in laboratory values will be presented in Figure 21, Figure 22, Figure 23, Figure 24, Figure 25, Figure 26, and Figure 27.

Subject visits with abnormal laboratory results, Grade 1 severity or higher, will be presented in Table 46 and Table 47.

Listing 11 and Listing 12 will provide a complete listing of individual clinical laboratory results with applicable reference ranges.

9.7. Vital Signs and Physical Evaluations

Vital sign measurements include pulse, systolic blood pressure, diastolic blood pressure and oral temperature. Vital signs are assessed at Day 1, Day 8, Day 15, Day 29, Day 36, Day 43, Day 180, Day 187, and Day 194. Vital signs will be tabulated by visit, treatment group, and maximum severity (Table 73, Table 74, Table 75,

Table 76, and Table 77) and listed by subject (Listing 13). The vital signs grading scale is presented in Table 7.

Physical Examinations are performed only at screening and where indicated based upon timing and/or symptoms at follow-up visits. Such indicated physical examinations, if performed, will be presented in Listing 14. Physical Examinations will include assessments of the following organs and organ systems: skin, head, eyes, ears, nose, and throat, neck, lungs, heart, liver, spleen, abdomen, extremities, lymph nodes (axillary and cervical), and nervous system.

9.8. Concomitant Medications

Concomitant medications will be coded to the Anatomical Therapeutic Classification using the WHO Drug Dictionary. The use of prior and concomitant medications taken during the study will be recorded on the eCRFs. A by-subject listing of concomitant medication use will be presented (Listing 15). The use of concomitant medications during the study will be summarized by ATC1, ATC2 code and treatment group for the Safety population (Table 78).

9.9. Other Safety Measures

Not applicable.

10. PHARMACOKINETICS

Not applicable.

11. **IMMUNOGENICITY**

See Section 8.

12. OTHER ANALYSES

Not applicable.

13. REPORTING CONVENTIONS

P-values ≥ 0.001 and ≤ 0.999 will be reported to 3 decimal places; p-values less than 0.001 will be reported as "<0.001" The mean, standard deviation, and other statistics will be reported to 1 decimal place greater than the original data. The minimum and maximum will use the same number of decimal places as the original data. Proportions will be presented as 2 decimal places; values greater than zero but <0.01 will be presented as "<0.01". Percentages will be reported to the nearest whole number; values greater than zero but < 1% will be presented as "<1%"; values greater than 99% but less than 100% will be reported as ">99%". Estimated parameters, not on the same scale as raw observations (e.g. regression coefficients) will be reported to 3 significant figures.

14. TECHNICAL DETAILS

SAS version 9.4 or above will be used to generate all tables, figures and listings.
15. SUMMARY OF CHANGES IN THE CONDUCT OF THE STUDY OR PLANNED ANALYSES

Not applicable.

17. LISTING OF TABLES, FIGURES, AND LISTINGS

Table, figure, and listing shells are presented in Appendices 1, 2, and 3.

APPENDICES

9.5.1 Immunogenicity and Safety Measurements Assessed and Flow Chart

Table 1:Schedule of Study Procedure

Study Visit	Screening	01	02	03	04	05	06	07	08	09	10	11	12	13	14	15	16	17	
Study day from 1 st vaccine	Screening (≤28 days) ^{a,b}	Day 1°	Day 4** +/-1	Day 8 +/-1	Day 15 +/-2	Day 29 +/-2	Day 32**	Day 36	Day 43	Day 57	Day 120**	Day 180 +/- 14	Day 184 **	Day 187	Day 194	Day 208	Day 270**	Day 360 +/-28	Early Termination/ Unscheduled
Study day from 2 nd vaccine						Day 1	Day 4** +/-1	Day 8 +/-1	Day 15 +/-2	Day 29 +/-2	Day 92** +/- 14								
Study day from 3 rd vaccine												Day 1	Day 4** +/-1	Day 8 +/-1	Day 15 +/-2	Day 29 +/-2	Day 90** +/-14	Day 180 +/- 14	
Obtain Informed Consent	X ^b																		
Medical History*	Х	Х				Х						Х							
Serum pregnancy test ^e	X																		
Urine pregnancy test ^e		\mathbf{X}^{h}				X ^h						$\mathbf{X}^{\mathbf{h}}$							{X}
Review of birth control history with female subjects	Х	Xe				Xe						Xe							Х
Counsel on pregnancy avoidance ^e	х	Х		Х	Х	Х		Х	Х	Х	Х	Х		Х	Х	Х			{X}
Physical examination ⁱ	Х	$\{X\}^h$		{X}	$\{X\}$	$\{X\}^h$		{X}	$\{X\}$	$\{X\}$		$\{X\}^h$		{X}	{X}	{X}		$\{X\}$	{X}
Vital signs ^j	Х	Х		Х	Х	Х		Х	Х			Х		Х	Х				{X}
Review of Eligibility Criteria	Х	X ^{c,h}				X ^h						X ^h							
Study Visit	Screening	01	02	03	04	05	06	07	08	09	10	11	12	13	14	15	16	17	

Study Visit	Screening	01	02	03	04	05	06	07	08	09	10	11	12	13	14	15	16	17	
Study day from 1 st vaccine	Screening (≤28 days) ^{a,b}	Day 1°	Day 4** +/-1	Day 8 +/-1	Day 15 +/-2	Day 29 +/-2	Day 32**	Day 36	Day 43	Day 57	Day 120**	Day 180 +/- 14	Day 184**	Day 187	Day 194	Day 208	Day 270**	Day 360 +/-28	Early Termination/ Unscheduled
Study day from 2 nd vaccine						Day 1	Day 4** +/-1	Day 8 +/-1	Day 15 +/-2	Day 29 +/-2	Day 92** +/- 14								
Study day from 3 rd vaccine												Day 1	Day 4** +/-1	Day 8 +/-1	Day 15 +/-2	Day 29 +/-2	Day 90** +/-14	Day 180 +/- 14	
Pre- Administration Reactogenicity Assessments		X ^h				X ^h						X ^h							
Randomization		\mathbf{X}^{h}																	
Study vaccine administration						▼						▼							
Distribution of memory aid		X^k				X^k						X ^k							
Review of subject diary/ solicited events by staff			Х	Х	Х		Х	Х	Х				Х	Х	X				{X}
AE/SAE Assessment ^m		Х	Х	Х	Х	Х	Х	Х	Х	Х	Х	Х	Х	Х	Х	Х	Х	Х	$\{\mathbf{X}\}$
Evaluate vaccination site		Х		Х	$\{X\}$	Х		Х	{X}			Х		Х	$\{X\}$				$\{X\}$
Post- Administration Reactogenicity Assessments		X				X						X							
Concomitant medications	X	X	X	X	X	X	X	X	X	X	X ¹	X	X	X	X	Х	X ¹	X ¹	X ¹
Hematology, chemistry ^f (mL)	13 ⁿ			13	{13}			13	{13}			13 ^h		13	{13}				{13}

Study Visit	Screening	01	02	03	04	05	06	07	08	09	10	11	12	13	14	15	16	17	
Hepatitis B surface antigen, hepatitis C antibody, HIV types 1 and 2 antigen/antibody	10																		
Urine drug screen	Х																		
Hepatitis E IgM and IgG antibodies	10																		
Serum: Immunogenicity (mL)		10 ^h		10	10	10 ^h		10	10	10		10 ^h		10	10	10		10	{10}
Study Visit	Screening	01	02	03	04	05	06	07	08	09	10	11	12	13	14	15	16	17	
Study day from 1 ^s vaccine	Screening (≤28 days) ^{a,b}	Day 1°	Day 4** +/-1	Day 8 +/-1	Day 15 +/-2	Day 29 +/-2	Day 32**	Day 36	Day 43	Day 57	Day 120**	Day 180 +/- 14	Day 184 **	Day 187	Day 194	Day 208	Day 270**	Day 360 +/-28	Early Termination/ Unscheduled
Study day from 2 nd vaccine						Day 1	Day 4** +/-1	Day 8 +/-1	Day 15 +/-2	Day 29 +/- 2	Day 92** +/- 14								
Study day from 3 rd vaccine												Day 1	Day 4** +/-1	Day 8 +/-1	Day 15 +/-2	Day 29 +/-2	Day 90** +/-14	Day 180 +/- 14	
Peripheral Blood Mononuclear Cells (PBMC) and Plasma Collection for Future Use		48 ^h		16	36	48 ^h		16	36	32		48 ^h		16	36	32		32	{≤48}
Total Blood Volume per visit (mL) ⁿ	33	58		39	{59}	58		39	{59}	42		71		39	{59}	42		42	{71}
Cumulative Blood Volume ⁿ	33	91		130	{189}	247		286	{345}	387		458		497	{556}	598		640	

Study Visit S	Screening	01	02	03	04	05	06	07	08	09	10	11	12	13	14	15	16	17	
---------------	-----------	----	----	----	----	----	----	----	----	----	----	----	----	----	----	----	----	----	--

▲ Prime dose: HEV 239 or Placebo; ▼Boost dose: HEV 239 or Placebo;

NOTE 1: In case of early withdrawal due to an adverse event, the investigator will collect all information relevant to the AE and safety of the subject, and will follow the subject to resolution, or until reaching a clinically stable endpoint. If feasible, blood will be drawn for immunologic assays. Subjects who wish to withdraw consent will be offered an optional visit for safety follow-up (before the formal withdrawal of consent). The subject has the right to refuse.

a) Screening may be split into multiple days or visits. This will include collection of baseline demographics and subject contact information.

b) Signing of the informed consent form (ICF) needs to be done before the first study-related activity.

c) The investigators should ensure that all study enrollment criteria have been met at the end of the screening period. If a subject's status changes (including laboratory results or the receipt of additional medical records) after screening but before Day 1 such that the subject no longer meets all eligibility criteria, then the subject should be excluded from participation in the study.
 d) Pre-study medications and therapies will be reviewed and recorded for the 30 days prior to the start of screening.

e) Subjects will be counselled to use adequate birth control methods to avoid pregnancy.

f) Baseline laboratories include complete blood count with differential (which will include white blood cells, absolute neutrophil count (ANC), absolute eosinophil count (AEC), hemoglobin, and platelets), creatinine, glucose, Alanine aminotransferase (ALT), hepatitis B surface antigen, hepatitis C antibody, HIV types 1 and 2 antigen/antibody, hepatitis E IgM and IgG antibodies, and urine drug screen (Protocol Section 2.3.1). Retesting of values that lead to exclusion is allowed once using an unscheduled visit during the screening period, provided there is an alternative explanation for the out of range value. If the initial laboratory screening occurred more than 28 days before baseline (Day 1) but the subject was unable to be vaccinated within the 28-day window (e.g., due to meeting Exclusion Criteria), the subject must have safety laboratories repeated (see protocol-specific Manual of Procedures (MOP) for details). Safety laboratories will be obtained on Days 8, 36, 180, and 187 will include complete blood count with differential (which will include white blood cells, ANC, AEC, hemoglobin, and platelets), Cr, and ALT (Protocol Section 2.3.1).

h) Prior to study vaccine administration.

i) An abbreviated physical examination will be carried out at screening. At other visits, symptom-directed examination will be performed as indicated by the investigator.

j) Includes heart rate, blood pressure and oral body temperature after at least 5 minutes rest. To be assessed prior to study vaccine administration and at a minimum of 30 minutes after study vaccine administration. At screening this will also include height and body weight for determination of body mass index (BMI).

k) When the memory aid is distributed to subjects, they will also be instructed as to when to contact the investigator about unsolicited AEs. Hypersensitivity symptoms will also be reviewed with the subject and they will be counselled that if any of these were occur they must contact study personnel or seek medical attention immediately.

1) Concomitant therapies between D57 and D150 and from D208 – D360 should only be recorded if administered in conjunction with SAEs.

m) Solicited AEs: Inclusive of solicited injection site reactions and systemic reactogenicity events performed on the day of each study vaccination through at least D8 after each study vaccination (see Protocol Sections 8.1.2). Unsolicited AEs: Collection of unsolicited AEs from time of first vaccination through D57; then from Day 180 – 208. SAEs: SAEs will be collected from the time of the first study vaccination through the last study visit (Day 360).

n) Volumes are the maximum volumes expected to be drawn. Samples may be fasted or non-fasted. The total volume at an unscheduled or early termination visit will not exceed the individual time point volume.

 $\{\ \}$ If indicated based upon timing and/or symptoms.

* See Protocol Section 7.1.1 regarding details of medical history to be collected.

** Telephone Visit

